### 8.3.3. Population of Interest

The secondary pharmacokinetic analyses will be based on the Pharmacokinetic population, unless otherwise specified.

### 8.3.4. Statistical Analyses / Methods

Details of the planned displays are provided in [Appendix 9](#) List of Data Displays and will be based on GSK Data Standards and statistical principles.

Unless otherwise specified, endpoints / variables defined in Section 8.3.1 will be summarised using descriptive statistics, graphically presented (where appropriate) and listed.

#### 8.3.4.1. Statistical Methodology Specification

The following pharmacokinetic statistical analyses will only be performed if sufficient data is available (i.e. if participants have well defined plasma profiles).

Endpoint / Variables
• Parent GSK2269557/Total radioactivity ratio for Cmax, AUC(0-t), AUC(0-24) and AUC(0-∞)
Model Specification
NOTE: The description below describes the current thinking of how to analyse these endpoints. The

proposed models will be assessed, and if not appropriate alternative models could be used.

[C]-GSK2269557/ Total radioactivity ratio for Cmax, AUC(0-t), AUC(0-24) and AUC(0-∞) - Period 1 IV Dose

Following sample analyses the Parent GSK2269557 for the IV dose is likely to be presented as [C]-GSK2269557 depending on the method, this is in addition to the Parent GSK2269557 for the inhaled dose and the total radioactivity. Analysis has been described for the [C]-GSK2269557 analyte however may be adapted if alternate sample analysis is conducted.

For each period, following loge-transformation of plasma pharmacokinetic parameters of [C]-GSK2269557 (from period 1 IV dose) and total radioactivity (from period 1 IV dose), AUC(0-∞), AUC(0-24), AUC(0-t) and Cmax will be separately analysed using a mixed effects model fitting a fixed effect term for analytes ([C]-GSK2269557 (from period 1 IV dose) and total radioactivity (from period 1 IV dose)) and a random effect for subject. The Kenward & Roger (KR) degrees of freedom approach will be used. Point estimates for the mean difference between the [C]-GSK2269557 and total radioactivity analytes, and associated 95% confidence interval will be constructed using the residual variance.

GSK2269557/ Total radioactivity ratio for Cmax, AUC(0-t), AUC(0-24) and AUC(0-∞) - Period 2 oral dose

Following sample analyses the Parent GSK2269557 will be presented as either GSK2269557 or [C]-GSK2269557 depending on the method, in addition to total radioactivity. Analysis has been described for parent GSK2269557 analyte and should be adapted to the appropriate analyte as appropriate.

For each period, following loge-transformation of plasma pharmacokinetic parameters of Parent GSK2269557 (from period 2 oral dose) and total radioactivity (from period 2 oral dose), AUC(0-∞), AUC(0-24), AUC(0-t) and Cmax will be separately analysed using a mixed effects model fitting a fixed effect term for analytes (Parent GSK2269557 (from period 2 oral dose) and total radioactivity (from period 2 oral dose)) and a random effect for subject. The Kenward & Roger (KR) degrees of freedom approach will be used.

Point estimates for the mean difference between the Parent GSK2269557 and total radioactivity analytes, and associated 95% confidence interval will be constructed using the residual variance.

### Model Checking & Diagnostics

- Model assumptions will be applied, but appropriate adjustments may be made based on the data
- The Kenward and Roger method for approximating the denominator degrees of freedom and correcting for bias in the estimated variance-covariance of the fixed effects will be used.
- Normality assumptions underlying the model used for analysis will be examined by obtaining a normal probability plot of the residuals and a plot of the residuals versus the fitted values (i.e. checking the normality assumption and constant variance assumption of the model respectively) to gain confidence that the model assumptions are reasonable.
- If there are any departures from the distributional assumptions, alternative models will be explored using appropriate transformed data

### Model Results Presentation

- Point estimates for the mean difference between the Parent GSK2269557 and total radioactivity analytes, and associated 95% confidence interval will be constructed using the residual variance. The point estimate and confidence interval will then be exponentially back-transformed to obtain point estimates and associated 95% confidence interval for the ratio Parent GSK2269557/total radioactivity. These will be presented in a tabular form.

### Sensitivity Analyses

- Data will be reviewed and if there are deviation that may affect the PK results, sensitivity analyses may be conducted as appropriate which may include excluding individual time points or excluding individual subjects as appropriate.

## **9. EXPLORATORY ANALYSES**

As outlined in the protocol, there is an exploratory endpoint of characterisation and quantification of metabolites in plasma, urine, faeces, and duodenal bile. These analytical investigations may be conducted by GSK PTS IVIVT and the results reported in a separate GSK PTS IVIVT report.

## 11. APPENDICES

### 11.1. Appendix 1: Protocol Deviation Management

- As detailed in Section 4.1, Protocol deviations will be tracked by the study team throughout the conduct of the study in accordance with the Protocol Deviation Management Plan and a listing and summary of important Protocol Deviations will be provided.
- A Per Protocol Population is not being defined for this study. However additional exploratory sensitivity summaries may be considered, if there are protocol deviations that may affect the primary PK endpoints. Any additional sensitivity summaries will be documented in the CSR.

## 11.2. Appendix 2: Schedule of Activities

### 11.2.1. Protocol Defined Schedule of Events

#### Schedule of activities for Treatment Period 1

Procedure	Screening		Treatment Period 1 (IV and inhaled dosing)								
			Day								
	-30 to -1	-1	1		2	3	4	5	6	7	8
			Pre-dose	Post-dose 0–16 h	24 h	48 h	72 h	96 h	120 h	144 h	168 h
Admission to Unit		X									
Informed Consent		X									
Discharge from Unit											X
Demographics		X									
Full Physical Exam		X									
Brief Physical Exam			X								X
Inhaler training 			X								
Medical/medication/drug/alcohol history		X									
HIV, Hep B and Hep C screen		X									
Alcohol and cotinine tests, and urine drugs of abuse 	X	X									
Laboratory safety tests	X	X	X		X						X
12-lead ECG 	X	X	X	X	X						X
Vital signs (HR and BP) 	X	X	X	X	X						X
Inhaled dose				X							
IV infusion				X 							
Local tolerability assessment 				X	X	X					
Blood samples for background radiation, total radioactivity, [  C]-GSK2269557 analysis and cold GSK2269557 analysis 	X 	X 	X 	X	X	X	X	X			X
Blood samples for metabolite profiling			X 	X 							
Urine collection 			X	X	X	X	X	X	X	X	X
Faecal collection 			X 	X	X	X	X	X	X	X	X
Entero-Test 			<————→								
Meals 				X							

Procedure	Screening		Treatment Period 1 (IV and inhaled dosing)								
			Day								
	-30 to -1	-1	1 Pre-dose	2 Post-dose 0–16 h	24 h	48 h	72 h	96 h	120 h	144 h	168 h
AE/concomitant medication review 			←	→							

1. Training conducted by reviewing the Patient Information Leaflet with the participant. Additional training may be conducted at the discretion of the investigator.
2. Breath test will be performed to check alcohol consumption. Both CO breath tests and urine cotinine tests will be performed to check smoking state.
3. Triplicate measurements will be taken at screening and pre-dose on Day 1; single measurements will be taken at 6 h post-dose on Day 1 and at all other time points. Mean of triplicate measurements to be used as baseline.
4. IV infusion to begin as soon as possible (but within 5 min) after the start of the inhaled dose.
5. Local tolerability assessment for injection site reactions will be performed immediately after the end of dosing on Day 1 at 6 and 12 h, and on Days 2 and 3.
6. Sampling times relative to the start of the IV infusion. Blood samples for total radioactivity, [C]-GSK2269557 analysis and cold GSK2269557 analysis will be taken: pre-dose and at 0h (post inhalation and pre-IV infusion), at the end of infusion and at 0.33, 0.5, 0.75, 1, 2, 3, 4, 6, 8, 12, 16, 24, 48, 72, 96 and 168 h after the start of infusion.
7. Background radiation sample taken at screening, Day -1 and pre-dose only.
8. An additional pre-dose blood sample may be taken from 1 participant for preparation of a plasma shipment control (details provided in the SRM).
9. Blood samples for plasma metabolite profiling will be collected at 0.5 h and 4 h after the start of the IV infusion.
10. An aliquot from each urine collection will be taken for metabolic profiling (separate study).
11. Sampling times relative to the start of the IV infusion. Urine will be collected at pre-dose, 0-6 h, 6-24 h then over 24 h collection periods as follows: 24-48 h, 48-72 h, 72-96 h, 96-120 h, 120-144 h, 144-168 h.
12. An aliquot from each homogenised faecal collection will be taken for metabolic profiling (separate study).
13. Sampling times relative to the start of IV infusion The pre-dose faecal collection sample can be collected up to 24 h pre-dose. Afterward faeces will be collected over 24 h collection periods as follows: 0-24 h, 24-48 h, 48-72 h, 72-96 h, 96-120 h, 120-144 h, 144-168h.
14. Entero-Test string device will be swallowed at approximately 3.5 h pre-dose (start of inhaled dose) while participants are in a fasted state and the string removed at about 2.5 h post-dose on Day 1. At about 0.5 h post-dose (i.e. 2 hours before string withdrawal) a food cue will be used to stimulate gall bladder emptying).
15. Meal times are 30 min, 4 h and 10 h post dose on Day 1. On all other days, meals will be served at the standard times for the unit.
16. AEs and SAEs will be collected from the signing of the ICF until the follow-up visit. However, any SAEs related to study participation or a GSK concomitant medication will be recorded from the time a participant consents to participate in the study and until the final follow-up visit contact.

## Schedule of activities for treatment period 2

Procedure	Treatment Period 2 (Oral dosing)									Follow-up (7-14 days post-last dose) 	
	Day										
	-1	1 		2	3	4	5	6	7		
		Pre-dose	Post-dose 0-16 h	24 h	48 h	72 h	96 h	120 h	144 h	168 h	
Admission to Unit	X										
Discharge from Unit 										X	
Drugs of abuse	X										
Alcohol and cotinine tests 	X										
Brief Physical Exam		X								X	
Laboratory safety tests	X	X		X						X X	
12-lead ECG	X	X	X 	X						X X	
Vital signs (HR and BP)	X	X	X 	X						X X	
Oral dose			X								
Blood samples for total radioactivity, [  C]-GSK2269557 analysis and cold GSK2269557 analysis		X 	X	X	X	X	X			X	
Blood samples for metabolite profiling		X	X 	X							
Urine collection 		X	X	X	X	X	X	X	X		
Faecal collection 		X 	X	X	X	X	X	X	X	X 	
Meals 			X								
AE/concomitant medication review 	<—————→										

1. There will be a washout of at least 14 days between dosing in treatment period 1 and 2.
2. If less than 1% of the dose is excreted in each 24 h period on Day 6 (120-144 h) and Day 7 (144-168 h) for a given participant, the participant may be discharged as early as Day 8 (after the LSC results are available), and no further samples (apart from for laboratory safety tests) will be collected. Follow-up procedures may be done at discharge and procedures scheduled for Day 8 and follow up will only be done once.
3. If excretion is higher than 1%, or if the results are inconclusive in each 24-h period on Day 6 (120-144 h) and Day 7 (144-168 h) for a given participant, that participant will remain at the unit, and urine and faecal collections will continue at 24-h intervals, for up to 7 days (until the morning of Day 15), until excretion is less than 1%. All remaining participants will be discharged from the unit on Day 15. Follow-up procedures may be done at discharge. In the unlikely event that excretion is still higher than 1% upon discharge on Day 15, participants will continue to collect faecal samples only, at home, at 24-h intervals. Samples collected at home will be returned to the clinic every 2-3 days.
4. Breath test will be performed to check alcohol consumption. Both CO breath tests and urine cotinine tests will be performed to check smoking state.
5. Vital signs and ECG will be taken 6 h post dose.
6. Sampling times relative to the oral dose. Blood samples for total radioactivity, [C]-GSK2269557 analysis and cold GSK2269557 analysis will be taken: pre-dose and at 0.25, 0.5, 0.75, 1, 2, 3, 4, 6, 8, 10, 12, 16, 24, 48, 72, 96 and 168 h post-dose.
7. Blood samples for plasma metabolite profiling will be collected at 2 h and 6 h post-[C]-GSK2269557 oral dose.
8. An aliquot from each urine collection will be taken for metabolic profiling (separate study).
9. Urine will be collected at pre-dose, at 0-6 h, 6-24 h then over 24 h collection periods as follows: 24-48 h, 48-72 h, 72-96 h, 96-120 h, 120-144 h, 144-168 h.
10. An aliquot from each faecal collection will be taken for metabolic profiling (separate study).
11. The pre-dose faecal sample can be collected up to 24 h pre-dose. Afterward faeces will be collected over 24 h collection periods as follows: 0-24 h, 24-48 h, 48-72 h, 72-96 h, 96-120 h, 120-144 h, 144-168 h.
12. If dose excretion is still higher than 1% after day 15 the participants will continue to collect faecal samples only, at home, at 24-h intervals until excretion is less than 1%.
13. Meal times are 4h and 10h post dose on Day 1. On all other days, meals will be served at the standard times for the unit.
14. AEs and SAEs will be collected from the signing of the ICF until the follow-up visit. However, any SAEs related to study participation or a GSK concomitant medication will be recorded from the time a participant consents to participate in the study and until the final follow-up visit contact.

### 11.3. Appendix 3: Study Phases and Treatment Emergent Adverse Events

#### 11.3.1. Study Phases

Assessments and events will be classified according to the time of occurrence relative to the start and/or stop time/date of the study treatment within the period (for period 1 the inhaled and IV dose, for period 2 the oral dose).

These treatment phases are already defined in the Time and Event table in [Appendix 2 Schedule of Activities](#) (Section [11.2](#)).

Treatment Phase	Definition
Pre-Treatment	Date/Time ≤ Study Treatment Start Date/Time
On-Treatment	Study Treatment Start Date/Time < Date/Time ≤ Study Treatment Stop Date/Time
Post-Treatment	Date/Time > Study Treatment Stop Date /Time

##### 11.3.1.1. Study Phases for Concomitant Medication

Study Phase	Definition
Prior	If medication end date is not missing and is before screening visit
Concomitant	Any medication that is not a prior

**NOTES:**

- Please refer to [Appendix 6: Reporting Standards for Missing Data](#) for handling of missing and partial dates for concomitant medication. Use the rules in this table if concomitant medication date is completely missing.

### 11.3.2. Treatment Emergent Flag for Adverse Events

Flag	Definition
Treatment Emergent	

• If AE onset date is on or after treatment start date & on or before treatment stop date plus washout.

• Study Treatment Start Date <math>\leq</math> AE Start Date <math>\leq</math> Study Treatment Stop Date + 14 days.

• For studies with greater than one treatment period (e.g., crossover study), if AE onset is during one period and worsens during a later period it would be counted in both periods. For the initial period the logic would be as above. For the later period the logic would use the treatment dates associated with the later period:

• Treatment Period Start Date <math>\leq</math> AE Worsening Date <math>\leq</math> Study Treatment Stop Date +14 days.

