Drugs of abuse	X										
Alcohol and cotinine tests ⁴	X										
Brief Physical Exam		X								X	
Laboratory safety tests	X	X		X					X	X	
12-lead ECG	X	X	X ⁵	X					X	X	
Vital signs (HR and BP)	X	X	X ⁵	X					X	X	
Oral dose			X								
Blood samples for total radioactivity, [¹⁴ C]-GSK2269557 analysis and cold GSK2269557 analysis		X ⁶	X	X	X	X	X		X		
Blood samples for metabolite profiling		X	X ⁷	X							
Urine collection ^{8,9}		X	X	X	X	X	X	X	X		
Faecal collection ^{10,11}		X ¹¹	X	X	X	X	X	X	X	X ¹²	
Meals ¹³			X								

Procedure	Treatment Period 2 (Oral dosing)									Follow-up (7-14 days post-last dose) ^{2,3}	
	Day										
	-1	1 ¹	2	3	4	5	6	7	8		
AE/concomitant medication review ¹⁴		←	→								

1. There will be a washout of at least 14 days between dosing in treatment period 1 and 2.
2. If less than 1% of the dose is excreted in each 24 h period on Day 6 (120-144 h) and Day 7 (144-168 h) for a given participant, the participant may be discharged as early as Day 8 (after the LSC results are available), and no further samples (apart from for laboratory safety tests) will be collected. Follow-up procedures may be done at discharge and procedures scheduled for Day 8 and follow up will only be done once.
3. If excretion is higher than 1%, or if the results are inconclusive in each 24-h period on Day 6 (120-144 h) and Day 7 (144-168 h) for a given participant, that participant will remain at the unit, and urine and faecal collections will continue at 24-h intervals, for up to 7 days (until the morning of Day 15), until excretion is less than 1%. All remaining participants will be discharged from the unit on Day 15. Follow-up procedures may be done at discharge. In the unlikely event that excretion is still higher than 1% upon discharge on Day 15, participants will continue to collect faecal samples only, at home, at 24-h intervals. Samples collected at home will be returned to the clinic every 2-3 days.
4. Breath test will be performed to check alcohol consumption. Both CO breath tests and urine cotinine tests will be performed to check smoking state.
5. Vital signs and ECG will be taken 6 h post dose.
6. Sampling times relative to the oral dose. Blood samples for total radioactivity, [¹⁴C]-GSK2269557 analysis and cold GSK2269557 analysis will be taken: pre-dose and at 0.25, 0.5, 0.75, 1, 2, 3, 4, 6, 8, 10, 12, 16, 24, 48, 72, 96 and 168 h post-dose.

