5.1.3. Follow-up

Follow-up procedures will be done 7–14 days after the last dose, and can be done on the day of discharge or at a separate visit.

The follow-up period may be extended if:

- radioactivity excretion is still higher than 1%
- a participant has an unresolved AE at the follow-up visit, which, in the opinion of the investigator, merits further follow-up;
- new information becomes available that supports an extended follow-up period.

The investigator will decide on the nature of the extended follow-up. For example, participants may have a telephone follow-up at which they are asked about AEs, or participants may be asked to attend extra outpatient visits for additional monitoring of blood levels or, and for extra safety tests. The extra safety tests might include tests that are not described in this protocol. The investigator reserves the right, during or after the study, to repeat safety tests or to do any extra safety tests that are in the best interest of the participants. Those extra tests may or may not be described in this protocol.

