9.2.1. Time Period and Frequency for Collecting AE and SAE Information

- All SAEs will be collected from the signing of the ICF until the follow-up visit at the time points specified in the SoA (Section 2).
- All AEs will be collected from the signing of the ICF until the follow-up visit at the time points specified in the SoA (Section 2).
- Medical occurrences that begin before the start of study treatment but after obtaining informed consent will be recorded on the Medical History/Current Medical Conditions section of the CRF not the AE section.
- All SAEs will be recorded and reported to the sponsor or designee immediately and under no circumstance should this exceed 24 hours, as indicated in [Appendix 5](#). The investigator will submit any updated SAE data to the sponsor within 24 hours of it being available.
- Investigators are not obligated to actively seek AEs or SAEs in former study participants. However, if the investigator learns of any SAE, including a death, at any time after a participant has been discharged from the study, and he/she considers the event to be reasonably related to the study treatment or study participation, the investigator must promptly notify the sponsor.
- The method of recording, evaluating, and assessing causality of AEs and SAEs and the procedures for completing and transmitting SAE reports are provided in [Appendix 5](#).

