9.3. Treatment of Overdose

For this study, any dose of GSK2269557 greater than 2000 µg within a 24-hour time period will be considered an overdose. For [¹⁴C]-GSK2269557, an intravenous dose of

100 µg or an oral dose of 4000 µg within a 24-hour time period will be considered an overdose.

GSK does not recommend specific treatment for an overdose. The Investigator (or physician in charge of the participant at the time) will use clinical judgment to treat any overdose.

In the event of an overdose, the Investigator (or the treating physician) should:

- Contact the Medical Monitor immediately.

Closely monitor the participant for AE/SAE and laboratory abnormalities until [¹⁴C]-GSK2269557 can no longer be detected systemically (at least 14 days).

Obtain a plasma sample for PK analysis within 14 days from the date of the last dose of study treatment if requested by the Medical Monitor (determined on a case-by-case basis).

Document the quantity of the excess dose as well as the duration of the overdosing in the CRF.

Decisions regarding dose interruptions or modifications will be made by the investigator in consultation with the Medical Monitor based on the clinical evaluation of the participant.

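### Both treatments get a 14-day treatment-emergent window, but adverse events after the oral dose may be collected for only 7 days, and at the minimum washout the two windows share the oral dosing day

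*SAP*

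**What the plan says.** **Flag.** RAP 11.3.2 counts an event as treatment emergent from treatment start to a date "on or before treatment stop date plus washout", and its formula line sets the limit at "Study Treatment Stop Date + 14 days". The later period uses its own treatment dates with the same 14 days. A note to that section asks that dosing and event times be taken into account, if they are collected.

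**Collection.** Protocol 9.2.1: "All AEs will be collected from the signing of the ICF until the follow-up visit". After that, investigators need not actively look for events in former participants, although related serious events that they learn of must still be reported.

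**End of collection after the oral dose.** Protocol 5.1.3: "Follow-up procedures will be done 7–14 days after the last dose", on the day of discharge or at a separate visit. Under the Period 2 schedule (Protocol 2, footnote 2), a participant excreting less than 1% of the dose on each of Days 6 and 7 may leave on Day 8, and "Follow-up procedures may be done at discharge and procedures scheduled for Day 8 and follow up will only be done once".

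**After Period 1.** Protocol 2, Period 2 footnote 1: "There will be a washout of at least 14 days between dosing in treatment period 1 and 2". Event collection stays open throughout that interval.

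**The concern.** The RAP applies one 14-day window to two treatments whose observed time can differ by a factor of two. A reader of the by-treatment summaries may take the flag to mean 14 observed days in both periods. For a participant followed up on Day 8 of the oral period, an event starting in the second week is not asked about. How long a man is observed after the oral dose also depends on how fast he excretes radioactivity, which is itself a study outcome.

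Incidence of adverse events is a secondary endpoint for the IV, oral and inhaled doses, and the oral route had not been tested in humans before (Protocol 5.5.1).

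There is also a boundary problem. The Period 1 window closes on a calendar date that can be the oral dosing date, so a new event that day can be flagged to both treatments. This is separate from the RAP's deliberate rule that an event which worsens in a later period counts in both.

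**Working it through.** **1. Days observed.** Inputs: Day 8 is 168 h and Day 15 is 336 h after dosing (Protocol 2 and 5.1.2); the window is 14 days (RAP 11.3.2); 6 participants are planned (Protocol 5.2).

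168/24 = 7 days and 336/24 = 14 days, which reproduces the 7 to 14 day range in Protocol 5.1.3.

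Coverage = days in the collection period / 14:

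- Period 1, participant who proceeds to Period 2: at least 14, so 14/14 = 100%.
- Oral, follow-up on Day 8: 7/14 = 50%.
- Oral, follow-up 10 days after the dose: 10/14 = 71%.
- Oral, follow-up on Day 15: 14/14 = 100%.

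In the extreme case the protocol allows, with all six followed up on Day 8, the oral window contains 6 × 7 = 42 observed participant-days, against 6 × 14 = 84 for Period 1.

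**2. What that could do to recorded incidence.** The documents give neither event rates nor onset times, so these figures are illustrations. Let p14 be the true 14-day incidence and s the assumed share of the 14-day hazard that falls after day 7. Closing collection at 7 days records

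p7 = 1 − (1 − p14)^(1 − s).

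| Assumed s | p14 | p7 | Relative loss |
|---|---|---|---|
| 0.50 (constant hazard) | 10% | 5.1% | 49% |
| 0.50 | 20% | 10.6% | 47% |
| 0.50 | 30% | 16.3% | 46% |
| 0.50 | 50% | 29.3% | 41% |
| 0.25 | 30% | 23.5% | 22% |
| 0.25 | 50% | 40.5% | 19% |
| 0.10 | 30% | 27.5% | 8.5% |
| 0.10 | 50% | 46.4% | 7% |
| 0 | any | p14 | 0 |

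With six participants these are small counts. At p14 = 30% and constant hazard, the expected number with an event falls from 6 × 0.30 = 1.80 to 6 × 0.163 = 0.98.

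**3. Overlap by date.** Let Period 1 dosing be on date D. Treatment lasts one day (RAP 11.5.2), so the stop date is also D and the Period 1 window runs from D to D + 14. The earliest permitted oral date is D + 14. An event starting on D + 14 then satisfies D ≤ D + 14 ≤ D + 14 for Period 1, and also meets the start condition for the oral period. With an oral date of D + 15 or later, a new event on the oral dosing day is outside the 14-day formula for Period 1. Dose times are recorded (Protocol 7.6), but the documents do not say that event times are.

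**The case against.** Much of the case on the other side stands.

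- **No comparison is planned.** RAP 2.4 rules out hypothesis tests and treatment comparisons. A reader might infer that a comparison of oral with inhaled plus IV is biased; the study makes no such comparison. The description of each treatment is still affected.
- **Early closure is permitted, not required.** Both Day 8 discharge and merged follow-up are options, and a participant kept to Day 15 is fully covered.
- **The documents do not establish 14 days as the duration of drug effect.** That inference is tempting because the washout and the overdose monitoring period share the figure. But the washout separates dosing periods, the monitoring rule applies only after an overdose (Protocol 9.3), and repeat testing of abnormal laboratory values uses 7 days (Protocol 9.4.4).
- **Late events may be few.** Cough in earlier studies came immediately after inhalation (Protocol 3.3.1). Predicted oral exposure is well below that of Period 1: Cmax 0.47 against 3.5 ng/mL, and AUC(0–24 h) 3.7 against 14.7 ng.h/mL (Protocol 5.5.1).
- **Period 1 is not perfectly observed.** No contact is scheduled between Day 8 discharge and readmission, so later events rely on recall. A participant who withdraws after Period 1 may have less than 14 days.
- **The flag may be only an outer limit.** It equals the latest scheduled follow-up, and the planned tables (RAP 11.9.7) cover all adverse events, with none titled treatment emergent. But those tables rest on the same unequal collection, and the RAP provides neither a common window nor a report of observation time.
- **The overlap is narrow.** It needs a washout of exactly 14 days, and the RAP note resolves it where event times exist.

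A reader might also see a fault in partner-pregnancy collection ending at follow-up (Protocol 9.2.5). It matches the contraception period in Protocol 6.1 and is not an inconsistency.

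**Conclusion.** The mismatch is real but conditional. Events after the oral dose can be observed for as little as 7 of the 14 days that the RAP flags, against at least 14 days, partly by recall, for participants who proceed from Period 1. It matters only for participants followed up before Day 15, and only for events starting after that visit.

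The effect is confined to descriptive incidence by treatment in six people. Its size cannot be derived from the documents and may be nil. It would be wrong to say that oral incidence is understated by half: a loss near that (41–49%) needs an assumed constant hazard over 14 days after a single dose, and with 10% of the hazard after day 7 the loss is about 7–9%.

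The double flag is certain by date at exactly the minimum washout, unless event clock times are collected and used. Both points merit correction because the change is small.

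**What to change.** **In the RAP:**

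1. End the Period 1 treatment-emergent window at the start of oral dosing if that comes before 14 days have elapsed. Assign events starting on the oral dosing day by clock time, and state in advance what is done if the time is missing.
2. Keep the planned tables of all adverse events. Beside them, add a by-treatment summary over a common 0–168 h from dosing in both periods, and report the actual observation time for each participant and treatment. If event times are not available, use the same calendar-day cut-off in both periods.

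The cost is wording and one extra table. Because the new summary is added and does not replace the others, no event leaves the main safety tables.

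**Optional, in the protocol:** reconcile the 7 to 14 day end of collection with the 14-day window through one adverse-event telephone contact 14 days after the oral dose, for participants followed up earlier. This needs a protocol change, because Protocol 5.1.3 mentions a telephone contact only as an example of extended follow-up. The cost is at most six short calls.
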